#### Figure 1 Study Overview

Abbreviations: BID: twice daily; CR: complete response; DLT: dose-limiting toxicity; DOR: duration of response; DCR: disease control rate; N: number; ORR: overall response rate; OS: overall survival; PD: progressive disease; PFS: progression-free survival; PK: pharmacokinetic; PR: partial response; SD: stable disease

The study is being conducted in two phases, with the Dose Optimization Phase (DOP) used to identify a dose for further evaluation in the Expansion Phase. The DOP has been completed and 75 mg BID with a mandatory dose reduction after 2 cycles to 25 mg BID was selected for the Expansion Phase. The primary overall response rate (ORR) endpoint will be assessed according to the Lugano criteria (Cheson et al, 2014). ORR in the DOP was based on investigator assessment, while ORR in the Expansion Phase will be determined by an Independent Review Committee.

### Table 1:Dose Optimization Phase Schedule of Events

				Cycle	/ Day						
	Screen-	Cycle 1			Сус	ele 2	Cycle 4 and then every 2 cycles 	End of Treat- ment (EOT) 	Safety Follow- up	PD Follow- Up 	Survival Follow- up 
Procedure 	ing D-30 to -1 	D1 	D8 ± 3	D15 ± 3	D1 ± 3	D15 ± 3	D1 ± 4	≤7 d from last dose	30 + 7 d from last dose	Q2M (± 1M)	Q3M (± 1M)
Provision of written informed consent	X										
Demographics	X										
Medical History, including cancer history	X										
12-lead electrocardiogram	X										
Echocardiogram	X										
Complete physical examination	X							X			
Targeted physical examination		X			X		X		X	See Table 3	
Vital signs 	X	X			Х		X	X	X		
Screening serology9	X										
Blood chemistry	X	X	X	X	X	X	X	X	X		
Hematology	X	X	X	X	X	X	X	X	X		
β-hCG pregnancy test 	X	X			X		X	X	X		
Serum Immunoglobulins	X	X					X	X			
Tumor tissue	X 										
Blood for pharmacodynamic assessment		X 			X 	X 					

				Cycle	/ Day						
		Cycle 1			Cycle 2		Cycle 4 and then every 2 cycles 	End of Treat- ment (EOT) 	Safety Follow- up	PD Follow- Up 	Survival Follow- up 
Procedure 	ing D-30 to -1 	D1 	D8 ± 3	D15 ± 3	D1 ± 3	D15 ± 3	D1 ± 4	≤7 d from last dose	30 + 7 d from last dose	Q2M (± 1M)	Q3M (± 1M)
Blood for pharmacokinetic assessment	See Table 5	See Table 5									
Blood for exploratory biomarkers 	X	X			X		X			Х	
Response Assessments						See Table 2					
ECOG Performance Status						See Table 5					
Concomitant medications & Procedures	All con	All concomitant medications and procedures are to be documented from 30 days before the Screening visit through 30 days after the last study drug dose							Х		
AE/SAE assessment	All AEs ar	All AEs are to be documented the time written informed consent is provided through 30 days after the last study drug dose							e last study		
Study Drug Administration		Duvelisib is to be administered PO BID continuously in 28-day cycles									
Survival status											X

Abbreviations: AE = adverse event; BID = twice daily; CMV = cytomegalovirus; d = day; D = Study Day; ECOG = Eastern Cooperative Oncology Group; EOT = End-of-Treatment; HIV = human immunodeficiency virus; HTLV-1 = human T-lymphotropic virus type 1; M = month; PD = progressive disease; PO = orally; Q2M = every 2 months; SAE = serious adverse event;  $\beta$ -hCG =  $\beta$ -human chorionic gonadotropin.

- 1. See Section 6 for additional information on each assessment.
- 2. Screening evaluations other than clinical laboratory tests performed within 7 days of C1D1 do not need to be repeated at C1D1 (predose). C1D1 laboratory tests do not need to be repeated if performed within 72 hours prior to Screening.
- 3. All laboratory samples on C1D1 should be collected predose.
- 4. Additional visits may be scheduled / procedures may be performed at the Investigator's discretion, as clinically indicated.
- 5. The End-of-Treatment (EOT) visit is to be performed within 7 days after the last study drug dose. If safety assessments were performed within the previous 2 weeks, they need not be performed at the EOT visit. If disease response assessments were performed within the previous 4 weeks, they need not be performed at the EOT visit.
- 6. Patients who discontinue treatment from duvelisib for reasons other than PD are to have disease response assessments performed Q2M per Table 3 until the development of PD, as determined by the Investigator, death, or initiation of alternate anti-cancer therapy.
- 7. After development of PD, as determined by the Investigator, patients are to be followed Q3M for survival; this follow-up may be conducted via telephone.
- 8. Vital signs, including temperature, blood pressure, and heart rate, are to be measured only if clinically indicated.

- 9. Screening serology includes assessment of CMV serologies and a liver serology panel. HIV and HTLV-1 tests are to be performed during Screening for all patients without documentation of prior negative results (see Section 6.10.1 for details).
- 10. Urine or serum β-human chorionic gonadotropin pregnancy testing is to be performed for women of childbearing potential. Pregnancy testing is to be repeated as deemed necessary by the Investigator.
- 11. Tumor biopsy from Screening or archival tumor tissue will be collected to evaluate prognostic markers. In the event a bone marrow biopsy is collected at Screening please provide a sample.
- 12. Blood collected at C1D1 (predose), C1D1 (1 hour postdose), C1D1 (4 hour postdose), C2D1 (predose), C2D15 (1 hour), C2D15 (4 hour) (Cohort 1, for patients receiving 50 mg on C2D15) and sent to the central laboratory.
- 13. To be sent to the central laboratory. Blood collected at predose on C1D1, C2D1, C4D1, and predose every 2 cycles thereafter.

# Table 2:Expansion Phase Schedule of Events

						Cycle / Day	y						
	Screen-		Cycle 1	Cycle 1		Cycle 2		Cycle 4 and then every 2 cycles (WCBP only)13	Cycle 5 and then every 2 cycles 	End of Treat- ment (EOT) 	Safety Follow- up	PD Follow- Up 	Survival Follow- up 
Procedure 	ing D-30 to -1 	D1 	D8 ± 3	D15 ± 3	D1 ± 3	D15 ± 3	D1 ± 3		D1 ± 4	≤7 d from last dose	30 + 7 d from last dose	Q2M (± 1M)	Q3M (± 1M)
Provision of written informed consent	X												
Demographics	X												
Medical History, including cancer history	X												
Archival Slides, initial pathological diagnosis	X 												
12-lead electrocardiogram9	X												
Echocardiogram 	X												
Complete physical examination	X									X			
Targeted physical examination		Х			X		X		X		X	See Table 4	
Vital signs 	X	Х	X	X	X	X	X		X	X	X		
Screening serology 	X												
CD4 lymphocyte cell count (local laboratory)	X												
Blood chemistry	X	X	X	X	X	X	X		X	X	X		
Hematology	X	X	X	X	X	X	X		X	X	X		
β-hCG pregnancy test 	Х	Х			Х		Х	Х	Х	X	Х		

						Cycle / Day	7						
	Screen-		Cycle 1			Cycle 2		Cycle 4 and then every 2 cycles (WCBP only)13	Cycle 5 and then every 2 cycles 	End of Treat- ment (EOT) 	Safety Follow- up	PD Follow- Up 	Survival Follow- up 
Procedure 	ing D-30 to -1 	D1 	D8 ± 3	D15 ± 3	D1 ± 3	D15 ± 3	D1 ± 3		D1 ± 4	≤7 d from last dose	30 + 7 d from last dose	Q2M (± 1M)	Q3M (± 1M)
Serum Immunoglobulins	X	X					Х		X	X			
Tumor tissue	X 												
Blood for pharmacodynamic assessment		X 				X 							
Blood for pharmacokinetic assessment								See Table 5	5				
Blood for exploratory biomarkers 	X	Х			X		Х		X			X	
Response Assessments				•				G T 11			1		
ECOG Performance Status								See Table 4	ł				
Concomitant medications & Procedures			All con	All concomitant medications and procedures are to be documented from 30 days before the Screening visit through 30 days after the last study drug dose								X	
AE/SAE assessment			All AEs	All AEs are to be documented at the time written informed consent is provided through 30 days after the last study drug dose									
Study Drug Administration				Duvelisib is to be administered PO BID continuously in 28-day cycles									
Survival status													Х

Abbreviations: AE = adverse event; BID = twice daily; CMV = cytomegalovirus; d = day; D = Study Day; ECOG = Eastern Cooperative Oncology Group; EOT = End-of-Treatment; HIV = human immunodeficiency virus; HTLV-1 = human T-lymphotropic virus type 1; M = month; PD = progressive disease; PO = orally; Q2M = every 2 months; SAE = serious adverse event;  $\beta$ -hCG =  $\beta$ -human chorionic gonadotropin.

1. See Section 6 for additional information on each assessment.

- 2. Screening evaluations other than clinical laboratory tests performed within 7 days of C1D1 do not need to be repeated at C1D1 (predose). C1D1 laboratory tests do not need to be repeated if performed within 72 hours prior to Screening.
- 3. All laboratory samples on C1D1 should be collected predose.
- 4. Additional visits may be scheduled / procedures may be performed at the Investigator's discretion, as clinically indicated.

- 5. The End-of-Treatment (EOT) visit is to be performed within 7 days after the last study drug dose. If safety assessments were performed within the previous 2 weeks, they need not be performed at the EOT visit. If disease response assessments were performed within the previous 4 weeks, they need not be performed at the EOT visit.
- 6. Patients who discontinue treatment from duvelisib for reasons other than PD are to have disease response assessments performed Q2M per Table 4 until the development of PD, as determined by the Investigator, death, or initiation of alternate anti-cancer therapy.
- 7. After development of PD, as determined by the Investigator, patients are to be followed Q3M for survival; this follow-up may be conducted via telephone.
- 8. Stained Formalin-fixed, paraffin-embedded (FFPE) slides used for PTCL diagnosis must be collected for all patients enrolled and submitted for central pathology review. See lab manual for details.
- 9. Additional on-treatment or follow-up electrocardiograms should be performed at the Investigator's discretion as clinically indicated.
- 10. Additional on-treatment or follow-up echocardiograms should be performed at the Investigator's discretion as clinically indicated.
- 11. Vital signs, including temperature, blood pressure, pulse, and respiration rate, and weight (kg) are to be measured. Height (cm) to be measured only at Screening.
- 12. Screening serology includes assessment of CMV serologies and a liver serology panel. HIV and HTLV-1 tests are to be performed during Screening for all patients without documentation of prior negative results (see Section 6.10.1 for details).
- 13. Urine or serum β-human chorionic gonadotropin pregnancy testing is to be performed for women of childbearing potential. Pregnancy testing is to performed monthly and may be repeated as deemed necessary by the Investigator. For cycles where pregnancy testing is the only requirement, the patient may have this done locally.
- 14. Tumor biopsy from Screening or archival tumor tissue will be collected to evaluate prognostic markers. In the event a bone marrow biopsy is collected at Screening please provide a sample.
- 15. Blood collected at C1D1 (predose), C1D1 (1 hour postdose), C1D1 (4 hour postdose), C2D15 (predose), C2D15 (1 hour), C2D15 (4 hour) and sent to the central laboratory. The collection of PD samples will occur for patients in the US only.
- 16. To be sent to the central laboratory. Blood collected at predose on C1D1, C2D1, C3D1, and predose every 2 cycles thereafter up to Cycle 11.

Table 3:	Dose Optimization	Phase Disease Res	ponse and Follow-up	Assessments
----------	--------------------------	--------------------------	---------------------	-------------

			Cycle 1			Cycle 4 and then every 2 Cycle 2 cycles 		End of Treatment (EOT) 	PD Follow- up 	Survival Follow- up 
Procedure 	Screening D-30 to -1	D1	D8 ± 3	D15 ± 3	D1 ± 3	D15 ± 3	D1 ± 4	≤ 7 d from last dose	Q2M (± 1M)	Q3M (± 1M)
PET-CT or CT or MRI 	X 				X 		X	Х	Х	
ECOG performance status	X						X	Х	Х	
Survival status										Х

Abbreviations: C = cycle; CT = d = day; D = Study Day; ECOG = Eastern Cooperative Oncology Group; EOT = End-of-Treatment; FDG = fluorodeoxyglucose; IRC = independent review committee; M = month; MRI = magnetic resonance imaging; PD = progressive disease; PET = positron emission tomography; PTCL = peripheral T-cell lymphoma; Q2M = every 2 months.

- 1. See Section 6.11 for additional information on disease response assessments.
- 2. Additional visits may be scheduled / procedures may be performed at the Investigator's discretion, as clinically indicated.
- 3. The EOT visit is to be performed within 7 days after the last study drug dose.
- 4. Patients who discontinue treatment from duvelisib for reasons other than PD are to have disease response assessments performed Q2M until the development of PD, as determined by the Investigator, death, or initiation of alternate anti-cancer therapy.
- 5. After development of PD, as determined by the Investigator, patients are to be followed Q3M for survival until closure of the study by the Sponsor; this follow-up may be conducted via telephone.
- 6. PET-CT is the preferred method of assessment. The modality chosen to evaluate response in each individual patient should be the same throughout the duration of the study. PET images are to be assessed using the 5-point scale (5PS). At each scheduled timepoint, the Investigator will be asked to provide a PET-CT-based response, based on the Lugano (Cheson et al. 2014) response criteria. Images will be centrally stored and read, with disease response determined by the IRC using the central image assessments.
- 7. To be performed within 14 days before C1D1. At Screening, disease will be assessed with PET-CT. Where PET-CT is not feasible, CT with contrast or MRI may be used after discussion with the Medical Monitor. Subsequently, for FDG-avid PTCL, PET-CT will be used to assess disease status and for FDG-non-avid PTCL, CT with contrast or MRI will be appropriate substitutes.
- 8. To be performed within 7 days prior to starting Cycle 2.

#### Table 4: Expansion Phase Disease Response and Follow-up Assessments

				Cycle	/ Day		-			
			Cycle 1		Сус	le 3	Cycle 5 and then every 2 cycles 	End of Treatment (EOT) 	PD Follow- up 	Survival Follow- up 
Procedure 	Screening D-30 to -1	D1	D8 ± 3	D15 ± 3	D1 ± 3	D15 ± 3	D1 ± 4	≤7 d from last dose	Q2M (± 1M)	Q3M (± 1M)
PET-CT or CT or MRI 	X7				X 		X	X	Х	
ECOG performance status	X						X	X	Х	
Survival status										X

Abbreviations: C = cycle; CT = d = day; D = Study Day; ECOG = Eastern Cooperative Oncology Group; EOT = End-of-Treatment; FDG = fluorodeoxyglucose; IRC = independent review committee; M = month; MRI = magnetic resonance imaging; PD = progressive disease; PET = positron emission tomography; PTCL = peripheral T-cell lymphoma; Q2M = every 2 months.

- 1. See Section 6.11 for additional information on disease response assessments.
- 2. Additional visits may be scheduled / procedures may be performed at the Investigator's discretion, as clinically indicated.
- 3. The EOT visit is to be performed within 7 days after the last study drug dose.
- 4. Patients who discontinue treatment from duvelisib for reasons other than PD are to have disease response assessments performed Q2M until the development of PD, as determined by the Investigator, death, or initiation of alternate anti-cancer therapy.
- 5. After development of PD, as determined by the Investigator, patients are to be followed Q3M for survival until closure of the study by the Sponsor; this follow-up may be conducted via telephone.
- 6. PET-CT is the preferred method of assessment. The modality chosen to evaluate response in each individual patient should be the same throughout the duration of the study. PET images are to be assessed using the 5-point scale (5PS). At each scheduled timepoint, the Investigator will be asked to provide a PET-CT-based response, based on the Lugano (Cheson et al. 2014) response criteria. Images will be centrally stored and read, with disease response determined by the IRC using the central image assessments.
- 7. To be performed within 14 days before C1D1. At Screening, disease will be assessed with PET-CT. Where PET-CT is not feasible, CT with contrast or MRI may be used after discussion with the Medical Monitor. Subsequently, for FDG-avid PTCL, PET-CT will be used to assess disease status and for FDG-non-avid PTCL, CT with contrast or MRI will be appropriate substitutes.
- 8. To be performed within 7 days prior to starting Cycle 3.

		Cycle / Day									
		Cycle 1		Cyc	le 2	Cycle 3	Cycle 5				
Procedure 	D1	D8 ± 3	D15 ± 3	D1 ± 3	D15 ± 3	D1 ± 3	D1 ± 4				
Dose Optimization Phase 	X 	X 	X 	X 	X 						
Expansion Phase 			X 		X 	X 	$X^4$				

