# 4.3. Duration of Patient Participation

The duration of patient participation is dependent on the patient's tolerance of and response to duvelisib; it is anticipated that patients will participate in the study for a minimum of  $\sim$ 3 months.

All patients will be screened for study eligibility within 30 days before the first study drug dose (i.e., Baseline, C1D1). Patients who are determined to be eligible will be enrolled in the study at Baseline and will receive duvelisib continuously in 28-day cycles. For the Dose Optimization Phase, it is anticipated that patients will receive at least 1 cycle of therapy. For the Expansion Phase, it is anticipated that patients will receive at least 2 cycles of therapy. Unlike the Dose Optimization Phase if the patient demonstrates progression and no dose modification was required for toxicity, the patient may re-escalate to 75 mg BID with a confirmatory scan after approximately 4 weeks of therapy. Patients will continue duvelisib until development of PD or intolerance or another discontinuation criterion is met, as determined by the Investigator; no maximum duration of therapy has been set. After discontinuation of duvelisib, all patients are to attend an End-of-Treatment (EOT) visit within 7 days after the last study drug dose and then a Safety Follow-up visit 30 days after the last study drug dose. Patients who have not experienced PD will continue to be followed for disease response as per Table 3 or Table 4 until development

of PD, as determined by the Investigator. Patients with documented PD, as determined by the Investigator, will be followed on an every 3-month basis for survival until closure of the study by the Sponsor; follow-up for survival may be conducted via telephone.

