# 8. **DISCONTINUATION CRITERIA**

#### 8.1. Withdrawal of Individual Patients from Study Drug

Duvelisib will be discontinued for any of the following reasons:

- Patient withdrawal of informed consent
- Disease progression (NOTE: In the Expansion Phase, patients may stay on therapy if PD occurs following mandatory dose reduction if criteria are met. See Sections 1.3 and 9.1.2)
- Clinical deterioration due to PD (at the discretion of the Investigator)
- Study drug interruption for > 42 days due to duvelisib-related toxicity (unless approved by study Medical Monitor).
- AE, such as unacceptable toxicity
- Pregnancy
- Termination of the study by the Sponsor
- Death
- Other reasons, including major protocol violation, noncompliance

The Investigator must determine the primary reason for a duvelisib withdrawal and record this information on the electronic case report form (eCRF). The patient will be observed after discontinuation according to the Schedule of Assessments and Events.

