#### 9.1.2. Expansion Phase

The duvelisib dose in the Expansion Phase will be:

Duvelisib PO at 75 mg BID for the first 2 cycles (cycle = 28 days) until the first response assessment (See Table 4). Then, dose will be reduced to 25 mg BID and administered in 28-day cycles.

If a subsequent assessment demonstrates progression and the patient did not require a dose modification due to toxicity, the dose can be re-escalated to 75 mg BID with a confirmatory scan after approximately 4 weeks of therapy. If the patient has progressive disease at the confirmatory scan, then the patient should be discontinued. Patients that re-escalate to 75 mg BID may remain at this dose level until the need for dose modification or the criteria for discontinuation is met.

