2.5.2 Expansion Phase

- TEAEs and changes in laboratory values
- DOR, for those patients with CR or PR, defined as the time from the first documentation of response to the first documentation of PD, as determined by the IRC, or death due to any cause
- PFS, defined as the time from the first dose of study treatment to the first documentation of PD, as determined by the IRC, or death from any cause
- DCR, defined as $CR + PR + SD \ge 8$ weeks, calculated using IRC-determined responses
- OS and deaths
- PK parameters of duvelisib and its metabolites

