5.2.2 Analyses of Secondary and Exploratory Efficacy Endpoints

5.2.2.1 Duration of Response

Duration of response will be analyzed both for patients with ORR (CR or PR) and for patients with CR.

- Main DOR Analysis: DOR will only be calculated for those patients with a CR or PR from time to first response to PD or death (if death occurs prior to PD). Patients who withdraw from the study for any reason prior to PD and patients who have ongoing response at the time of the data cut will be censored at the date of their last response assessment.
- Duration of complete response (DOCR): DOCR is calculated from the time of first CR and only includes patients who had at least one CR response. It is otherwise defined the same as the Main DOR endpoint.

Estimates of the 25th percentile, median, and 75th percentiles will be for each of these DOR endpoints will be presented using the Kaplan-Meier method. A 2-sided 95% confidence interval for median DOR will be provided by using the Brookmeyer-Crowley method. Kaplan-Meier plots will be provided.

In addition, the number and percent of patients with duration of response of at least 3 months, 6 months and 12 months will be tabulated.

A summary of time to first response will also be presented in patients who achieved CR or PR and in patients who achieved CR.

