5.2.2.3 Analysis of PFS

For the PFS analyses, censoring of PFS will be performed as detailed in Table 2. Note that progression may be documented based on scheduled or unscheduled disease status assessment, and that unscheduled disease status assessments will be included in calculating the gap between adequate disease status assessments.

PFS will be estimated for each cohort using the Kaplan-Meier method. PFS will be plotted by using the Kaplan-Meier method. Number of patients with events, type of events (progression or death), number of patients censored, number of patients for each reason of censoring, Kaplan-Meier estimates and 95% confidence intervals for the 25th percentile, median, and 75th percentile for PFS will be presented. A 2-sided 95% confidence interval for median PFS will be provided by using the Brookmeyer-Crowley method. Probabilities of remaining alive and progression free at selected time points may also be presented.

PFS analysis will be repeated for the subset of enrolled Japanese patients and for each of the prognostic factors described in section 4.5.2

Situation	Date of Event or Censoring	Outcome
No adequate baseline disease status assessment	Date of randomization + 1 day	Censored
No adequate post-baseline disease status assessment unless death occurs prior to first scheduled post-baseline assessment	Date of randomization + 1 day	Censored

Table 2: Primary PFS Censoring/Event Rule

No documented progression or death	Date of last adequate disease status assessment	Censored
Documented progression with ≤1 missing scheduled disease status assessment before progression	Date of the earliest assessment that results in a finding of unequivocal progression	Event
Death before progression being documented with ≤1 missing scheduled disease status assessment before death	Date of death	Event
Documented progression or death following a gap between adequate disease status assessments equivalent to 2 missed visits	Date of last adequate disease status assessment before the gap	Censored
New anticancer treatment or procedure started before documented progression or death.	Date of last adequate disease status assessment prior to start of new anticancer therapy	Censored

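### Expansion Phase imaging generally ends at Investigator PD while DOR and PFS count IRC PD; the SAP needs a sensitivity analysis for patients called PD by the Investigator only

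*Protocol*

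**What the plan says.** **Event definition.** SAP 2.5.2 assigns Expansion Phase progression to the IRC: "PFS, defined as the time from the first dose of study treatment to the first documentation of PD, as determined by the IRC", or death. The same section defines DOR in the same way.

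**When imaging ends.** Protocol Table 4 footnote 4 covers one group: "Patients who discontinue treatment from duvelisib for reasons other than PD are to have disease response assessments performed Q2M", and this continues "until the development of PD, as determined by the Investigator, death, or initiation of alternate anti-cancer therapy". For patients called PD while on treatment, the relevant texts are footnote 5 of that table and Protocol 4.3: "Patients with documented PD, as determined by the Investigator, will be followed on an every 3-month basis for survival". This contact may be by telephone.

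**When the IRC reads.** Protocol 4.1 places IRC determination at futility and at the end of the study, and SAP 3.5 adds reads for interim analyses. Neither document requires an IRC read before a patient's scans stop.

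**Exception.** Protocol 8.1 states: "In the Expansion Phase, patients may stay on therapy if PD occurs following mandatory dose reduction if criteria are met". Under Protocol 9.1.2, if no dose modification for toxicity was needed, "the dose can be re-escalated to 75 mg BID with a confirmatory scan after approximately 4 weeks of therapy".

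**Censoring.** In SAP 5.2.2.3 Table 2, the row "No documented progression or death" censors PFS at the last adequate assessment. A separate row censors at the last adequate assessment before new anticancer therapy. SAP 5.2.2.1 censors DOR at the last response assessment for "Patients who withdraw from the study for any reason prior to PD" and for responses still ongoing at the data cut. Neither section names the patient with Investigator PD but no IRC PD.

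**The concern.** One assessor's call ends the imaging and another assessor's call makes the event. If the Investigator sees progression that the IRC does not see on the same scan, there may be no later scan on which the IRC could call it. The patient then leaves the IRC risk set because progression looked close. Kaplan-Meier estimation assumes that censored patients face the same later hazard as those still followed, and that is doubtful here.

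This is a single-arm trial, so no control arm shares the distortion. Durability is reviewed alongside ORR at the futility look (Protocol 11.13). SAP 5.2.2.1 tabulates responses lasting at least 3, 6 and 12 months. SAP 3.5 says interim results will be used for regulatory submission and possible publication. An IRC median DOR that is too long would carry into all of these.

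**Working it through.** **No figure in the plan to reproduce.** The documents give no expected median, event count or IRC-Investigator discordance rate for DOR or PFS. The powered calculation concerns ORR and is not an input here.

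**Step 1: follow one patient through the rules.** Take a patient with Investigator PD and no IRC PD.
- *PFS:* with no death, or with new therapy started, the patient is censored at the last adequate assessment. A later death is an event if at most one scheduled assessment was missed and no new therapy began. After a gap equal to two missed visits, the patient is censored before the gap.
- *DOR:* if alive, the patient is censored at the last response assessment. A later death is an event with no gap or new-therapy limit, but it falls after the Investigator PD date and so also lengthens DOR.
- *Re-escalation:* there is at least one more scan, and possibly continued scheduled scans.

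**Step 2: upper bound.** Assume a constant hazard, a true IRC median of 6 months, and a share d of progressions censored at the moment they occur, with no later death counted and no scan continued. The observed hazard is (1 − d) times the true hazard, so the median is 6/(1 − d) and the 6-month probability is 0.5^(1 − d).
- d = 10%: 6/0.9 = 6.7 months; 0.5^0.9 = 54%
- d = 20%: 6/0.8 = 7.5 months; 0.5^0.8 = 57%
- d = 30%: 6/0.7 = 8.6 months; 0.5^0.7 = 62%

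The true 6-month probability is 50%.

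**Step 3: relax the bound for DOR.** Simulation with assumed inputs: true IRC median 6 months, Investigator PD 2 months before IRC PD in discordant patients, median 6 months from Investigator PD to death, follow-up of 6 to 30 months.

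| Median DOR (months) | d = 10% | d = 20% | d = 30% |
|---|---|---|---|
| Upper bound, 6/(1 − d) | 6.7 | 7.5 | 8.6 |
| All discordant patients censored at Investigator PD | 6.5 | 7.2 | 8.0 |
| Later deaths count, as in the SAP | 6.4 | 6.8 to 6.9 | 7.3 |
| Later deaths count, half still scanned | 6.2 | 6.4 | 6.6 |

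**Step 4: scheduled scans, wider inputs.** A second simulation compared the planned rules with scanning until IRC PD. It used 8-weekly scans and 200,000 patients per scenario. Assumed inputs were 10% to 40% of Investigator PD calls not shared by the IRC, latent median 3 to 6 months (PFS) or 6 to 12 months (DOR), 60% starting new therapy, and median 6 months from Investigator PD to death.

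| Scenario | Shift in PFS median (months) | Shift in DOR median (months) |
|---|---|---|
| IRC would call PD at the next scan; nobody re-escalates | +0.01 to +1.46 | +0.25 to +1.80 |
| Same, half continue scans | 0.00 to +0.59 | +0.13 to +0.86 |
| Disagreement unrelated to imminent progression | −0.06 to +0.43 | +0.02 to +0.27 |

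**The case against.** The strongest reply is that this is a modest gap in secondary, descriptive endpoints, and that the plan already softens it.

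- **Scans do not always stop.** Re-escalation with a confirmatory scan is open mainly to patients who did well enough to reach the dose reduction, which largely describes the DOR population. Table 4 also lists an end-of-treatment scan. This stands, and it reduces the effect. It does not remove it: re-escalation is optional, is limited to patients without a toxicity dose modification, and does not help footnote 4 patients who are already off drug.
- **Not everyone is censored.** Deaths still count, most broadly for DOR. This stands.
- **Related outputs are planned.** There are Investigator-based DOR and PFS, counts of PFS censoring by reason, and swimmer plots showing IRC responses beside the end-of-treatment reason. These make many discordant patients visible. However, the Investigator-based analyses change the responder set and response dates along with the PD dates. They cannot isolate how far the IRC estimate moves because imaging ended.
- **The remedy has its own bias.** It assumes the IRC would have called PD on the Investigator's date. In the Step 3 simulation it gives 5.8, 5.6 and 5.4 months against a true 6.0. This stands, and the result must be labelled accordingly.

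A reader might infer that imaging always ends at Investigator PD, that every such patient is censored, and that the bias always favours the drug by the Step 2 amounts. The documents do not support that. The re-escalation path and the death rules contradict the first two points. The direction is an expectation: some PFS scenarios shift slightly downward.

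**Conclusion.** The mismatch between the assessor who ends imaging and the assessor who defines the event is in the text, and no planned analysis isolates its effect. The resulting censoring is probably informative and is expected to lengthen IRC DOR and PFS.

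Its size cannot be stated from the documents. The figures of 6.7, 7.5 and 8.6 months are upper bounds under an assumed 6-month median and assumed discordance of 10%, 20% and 30%. Once deaths and continued scanning are allowed for, the shift is smaller. It is near zero when discordance is low or unrelated to imminent progression. Every simulated figure also rests on assumed survival after Investigator PD, and the Step 4 figures on an assumed rate of new therapy.

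The primary IRC ORR is not affected, and DOR and PFS carry no hypothesis test. This is a worthwhile, inexpensive addition to the SAP and does not challenge the design.

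**What to change.** Add to SAP 5.2.2.1 and 5.2.2.3 a sensitivity analysis that:

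- for DOR, keeps the same IRC responders and IRC response dates, and for PFS keeps the mITT set;
- counts as an event, at the Investigator PD date, any patient whose imaging ended after Investigator PD without IRC PD, including a patient who later started new therapy or died;
- states which Investigator PD date applies to a patient who re-escalated;
- reports the number of such patients;
- is shown beside the main IRC estimate and labelled a conservative (pessimistic) bound.

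The main IRC analyses stay as planned. The cost is a paragraph of SAP text, one further Kaplan-Meier run for each endpoint, and one count, all from data already collected. No extra scans or IRC reads are needed and patient management does not change. The sponsor must accept publishing an estimate that will be somewhat shorter than the main one if discordant patients exist. If there are few, the analysis shows that the IRC medians are robust.
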